
### Software

The analyses will be carried out in Stata (version 18 or later)[59] or R.

# Work package 2: Process Evaluation

# Objective

To assess SL in terms of the following (i) stakeholder acceptability (ii) pathways to impact, (iii) unintended and systemic consequences; (iv) barriers/facilitators; (v) equity assessment.

# Overall approach

The process evaluation will be primarily qualitative: n= 72 qualitative semi-structured interviews with stakeholders (tenants, landlords, implementers and representatives of stakeholder organisations); a national and a local workshop (n=10 for each); document analysis. Data collection will mostly focus on 4 'case' SL sites.

#### National stakeholder workshop

Early in WP2, we will hold an online workshop with national stakeholders (n=10) to assess views on how SL fits with national policy on housing and health. Through the workshop, we will develop our initial logic model (Appendix) into a more detailed map that provides a further breakdown of the intervention's core stages on the pathway to different impacts, situated in a wider system. To assist us, we will draw on strong structuration theory's framework, consisting of 4 elements: external

structures, internal structures, action/active agency and outcomes [60]. We will draw on this framework because it is designed to help users consider both agency and underlying (internal and external) structures; and because it can be used to consider multi-stage pathways to impact. We will focus particularly on equity impacts. The revised map will inform the rest of the work package, adapting an approach described in McGill et al, 2020 [61].

The national workshop will be asked to consider potential beneficial impacts, barriers and unintended consequences (including our own hypotheses on these: see above and also see logic model). As part of the exercise they will also be asked to think of systemic pathways to impacts not covered by our hypotheses. We ask specifically about equity impacts and about policy priorities and how they might be influenced by SL.

### Local stakeholder interviews, document analysis and workshop

We will then sample local stakeholders who can talk to us about how/if change in their area occurs in ways suggested by the National Workshop's systems map and hypothesised pathways. We will sample 4 SL schemes for qualitative fieldwork. The law distinguishes between smaller (up to 20% of homes) and larger schemes, so we will sample a smaller and larger scheme in both the North and South of England. Hackney, Newham, Gateshead and Liverpool meet this sampling criteria and have expressed interest. Data collection proposed for those case studies will be an upper limit of 72 semi-structured interviews: 18 per site (4 implementers, 2 from community organisations representing tenants, 4 PRS property managers/landlords, 8 tenants). Interviews approx. 1 hour; remote or F2F depending on interviewee preference. Tenants compensated for time with £20 shopping voucher + travel expenses fowor F2F.

We have also introduced a lower limit of 48 semi-structured interviews: 12 per site (2 implementers, 2 from community organisations representing tenants, 3 PRS property managers/landlords, 5 tenants). Criteria for lower limit will be (i) saturation; or (ii) sample frame being met. Sample frame (per site) = 1 senior and 1 front line implementer; 2 representatives from community organisations for tenants; 1 small, 1 medium and 1 large landlord; tenants must include men and women, people with and without child dependents, white and BAME ethnicity. The majority of tenants must have a smaller than average household income for their area. Contact questions during recruitment stage will establish these criteria.

Interviews approx. 1 hour; remote or F2F depending on interviewee preference. Tenants compensated for time with £20 shopping voucher + travel expenses for F2F.

Document analysis: includes reports, compliance and enforcement data, consultation documents, budgets for each site, landlord and tenant forums. Document analysis: includes reports, compliance and enforcement data, consultation documents, budgets for each site, landlord and tenant forums.

Online workshop with local stakeholders (n=10) to interpret early findings.

The interviews for the 4 case studies will provide local perspectives on SL from tenants, landlords, implementers and other stakeholders. Topic guides will vary by stakeholder group, focusing particularly on issues, experiences, hypotheses and impact pathways relevant to each type of stakeholder. However, they will each consider the following core themes: (i) stakeholder acceptability (ii) pathways to impact, (iii) unintended and systemic consequences; (iv) barriers/facilitators; (v) equity. We will ask stakeholders to talk about their own experiences and provide opportunities for them to give their views about the PRS, SL and its (equity) impacts.

### Recruitment and sampling.

We will recruit people from the following groups: national stakeholders, local implementers, PRS property managers/landlords, community organisations representing tenants, tenants.

- Our national workshop will include stakeholders identified using our current contacts and networks – with snowballing as required. National government includes Department for Levelling Up, Housing and Communities; Department of Health and Social Care; Office for Health Improvement and Disparities; Local Government Association. We may also include a minority of stakeholders responsible for larger regions: e.g. devolved regional authorities such as Greater London Authority. We also have contacts with national housing charities for a non-governmental perspective: e.g. Shelter and Crisis. We would expect a range of policy perspectives across this group.
- Interviews with local implementers will focus on the four case study sites. Job roles and
  management structures for each site will vary but in each we would recruit the SL lead, a
  frontline PRS regulator/inspector, an implementer overseeing finances, a public health
  representative. We would contact and invite interviewees through established contacts at
  each local authority.
- Interviews with representatives from landlords (small and large businesses), property managers and community organisations. We will have a dual approach. Firstly, we will ask the local authority leads to identify relevant stakeholders from these groups. Secondly, we will conduct our own bespoke search for relevant local stakeholders through google and social media forums (e.g. Facebook and Twitter), snowballing if necessary. We had previously assumed that local authority recommendations might lead us to stakeholders who are more supportive of SL, while our own search could identify stakeholders with a more critical stance. In practice, we found critical and supportive viewpoints from stakeholders identified through both these approaches.
- Interviews with tenants. In our experience this is the most difficult group to recruit from. We plan to begin by involving a community representative from each site to assist with our local recruitment strategy. We would recruit via local authority, community groups (online and physical), and advertising via face book and local newspapers. In each site we would ask for expressions of interest, and then make a follow-up contact (by phone, email, zoom depending on person's preference) to ask for some initial details. This is to help us ensure the following characteristics are varied in each site: age (retired vs working age); gender; disability and ethnicity. We will then select interviewees and begin a process of informed consent.
- Omissions. We think it likely that the worst offending (e.g. 'rogue/criminal') landlords will be
  unwilling to participate. We will prioritise recruitment of tenants experiencing some form of
  disadvantage: during our tenant recruitment process we will ask about their rent, property
  and household employment situation to identify tenants with low SES. This means we will
  hear less from affluent tenants. We also think it realistic to assume that some tenants,
  including some disadvantaged tenants, will be unaware or unwilling to participate in the
  study despite our best efforts.

### Duty of care

While our questions are not intended to be highly sensitive, we recognise that some participants may choose to describe experiences they find upsetting. Some – notably tenant participants – may ask researchers to help them with housing problems or other difficulties. We must recognise that the researchers are not experts in housing rights, nor are they qualified to give health related advice. We have prepared a short list of services and resources (see Appendix II) for researchers to offer to participants if required.

In terms of researcher safety, we intend to do most data collection remotely (e.g. phone or online) or in public settings. However, we will give weight to participant preferences, meaning that it is possible some interviews may occur in a participant's home. We have a protocol for fieldwork in

participant's' homes to ensure staff whereabouts are known and a response process is in place (see Appendix III).

#### Data collection

As stated above, the study involves a mixture of group workshops and individual semi-structured interviews. In the appendix we provide topic guides for (i) national workshop, (ii) local interpretive workshop, (iii) tenant interviews, (iv) landlord interviews, and (v) stakeholder interviews.

### Analysis and outputs

Analysis of qualitative data will include the following approaches. We will use the first workshop to help us (i) transform our initial logic model into a conceptual map of the wider system within which SL occurs; and (ii) finalise a list of hypothesised impact pathways (both beneficial and detrimental impacts). This will inform our topic guide development for the case studies [61]. During our analysis stage we will hold our second stakeholder workshop to present some early findings and ideas and learn from stakeholders responses to these.

Analysis of case study data will include different approaches leading to at least three peer review articles.

Article 1: To assess pathways to impact and their barriers and facilitators, we will draw on strong structuration theory's framework, consisting of 4 elements: external structures, internal structures, action/active agency and outcomes [60]. We have used it previously in an approach that combines document analysis with interview data – we will further develop this approach.

Article 2: Equity assessment. While article 1 will focus on the main pathways to impact, the second article will focus specifically on how and why differential impacts occur. Our plan is to again use the strong structuration approach to (i) identify and unpick a wide range of hypotheses (building on those we have already considered) to explain differential effects, and identify the social groups affected, intersections that may occur, and the agentic and structural factors underpinning the (re-)production of privilege and discrimination within the 'PRS system.'

Article 3: Equity – emergent theme(s). This article will be a more traditional thematic analysis of emergent themes. We are deliberately leaving this paper open, as we think a key benefit of qualitative research is that it helps researchers identify issues that were not necessarily prominent in our thinking at research planning stage. As we progress through our analysis for article 1 and 2, we will agree on a critical issue affecting health equity and focus on that issue in more detail for article 3. Ideally, we would like this to exemplify something we regard as crucial to the wider understanding of 'upstream interventions.' We are interested in exploring how system adaptation to housing and place interventions leads to unintended consequences. Providing we have capacity and resource, we may conduct a small number of additional or follow-up interviews to provide further data on the issue(s) we focus on (max. 10 extra participants).

# Work package 3: Economic evaluation *Objective*

To assess whether SL schemes are value for money.

### **Approach**

The economic evaluation will produce a cost-benefit analysis that uses the subjective wellbeing approach to monetise the benefits of SL. A cost-benefit analysis is better suited to assessing the

value of SL than a cost-effectiveness analysis. A cost-effectiveness analysis requires a comparison between alternatives, such as providing patients with a certain disease with usual treatment versus a new treatment. SL has no obvious alternative. Rather than informing policy makers about which of two options to choose to achieve an outcome that has already been agreed is worth achieving, the purpose of this economic evaluation is to inform policy makers whether this type of intervention is worth doing or if local governments' resources might be better spent on different programmes.

Using the subjective wellbeing approach to determine the monetary value of the benefits of SL avoids the problems of traditional preference-based methods of valuing non-market goods. The subjective wellbeing approach measures people's experiences instead of their preferences. It assesses the impact of non-market goods, policies, or events on how people think and feel about their lives as a whole. This impact is then converted into a monetary figure by comparing it to the effect of income on subjective wellbeing [62]. For example, if a policy increases subjective wellbeing by 0.5 on the 0 to 10 scale and similarly a £5,000 increase in income results in a 0.5 increase in subjective wellbeing, the value of the policy to the individual is assumed to be £5,000. The data on subjective wellbeing is being collected without any reference to the policy under consideration. Thus, the subjective wellbeing approach avoids the two main problems of stated preference methods which attempt to elicit individuals' "willingness to pay" for a particular outcome: When asking people how much they would be hypothetically willing to pay for a certain outcome, they tend to overstate their valuation of a good or they strategically misrepresent their true preferences [62]. The subjective wellbeing approach also avoids the problems of revealed-preference methods, which infer the implicit price of, for example, an environmental amenity by comparing the prices of houses that have similar characteristics except for the level of the environmental amenity. This method requires assuming that housing markets are in equilibrium, that individuals have full information on all house prices and characteristics and that there are zero transaction and moving costs. These assumptions are unlikely to be met [62].

If we measured the benefits of SL only in terms of QALYs or increases in employment rates or reductions in antidepressant prescribing costs to the NHS, we would miss the value of impacts that are difficult to measure but are potentially more important to people. Focusing on outcomes such as QALYs or employment captures the instrumental value but ignores the intrinsic value of improvements in housing quality.

The starting point for the calculation of the benefits of SL will be the estimate of the impact of SL on the life satisfaction variable from the APS, one of our secondary outcomes. We will then follow the procedure described in Dolan et al. (2019) [35]. Essentially, we will use an estimate of the impact of income on life satisfaction from previous research to determine the income change that would be required to achieve the same change in life satisfaction as achieved by SL. Multiplying this income change amount by the number of individuals affected by SL will provide the total benefit of SL. All our calculations will be retrospective and estimate the benefits of SL over our 2012 to 2019 sample period.

We will calculate the costs of SL from a public sector perspective. To determine the total cost of SL over the 2012 to 2019 sample period, we will measure the direct and indirect cost of SL in four case study sites. Accounting data provided by the case study sites will be the starting point for the cost calculation. However, the economic concept of opportunity cost goes beyond accounting cost. For example, local authorities might employ staff specifically for the administration of the SL schemes in their area, so these costs would be included in the accounting data as staff salaries and on-costs. However, staff not specifically employed for SL purposes might also be involved in administering local schemes. Any staff involved in SL will require office space and might need to be trained and supervised. Local authorities need to disseminate information about their SL schemes using their website or other means and maintain the online application system. All these activities incur costs, either directly in the

form of money being handed over in payment or indirectly in the form of resources such as staff time or office space not being available for alternative uses.

The four case study sites have been selected to represent different types of SL (smaller and larger) in different regional contexts (north and south). We will use extrapolation methods that use these two broad characteristics as well as cost information obtained through FOI requests to assign costs to the other local authorities that have implemented SL. We will subtract income from license fees to obtain net costs.

In addition, we will estimate the potential costs saved by the NHS through SL's impact on antidepressant prescribing, mental-health related hospital admissions and all-cause hospital admissions over our sample period. If possible, we will also estimate potential cost savings through impacts on mental health-related benefits. If we find substantial cost savings, we will subtract these from the cost of SL to local authorities to obtain net costs from a public sector perspective.

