# Intervention

This research protocol focuses on one type of regulatory intervention that local authorities have discretion to implement or not implement. The Housing Act 2004, and subsequent revisions in 2015, gave local authorities discretionary powers to implement **selective licensing (SL)** schemes [5]. SL requires landlords in geographically defined areas to pay for a 5-year licence. Fees vary but are around £600 [9,10]. The fees help finance the local authority's regulation of PRS in that area (e.g. housing inspections) although they may not cover the full costs to local authorities. When local authorities inspect PRS homes and find them to be substandard, landlords are expected to pay for the improvements necessary to meet the legal standards.

SL applies to privately rented properties occupied by a single household. Nine out of ten PRS homes meet this description. Houses that include multiple households (Houses in Multiple Occupation or HMOs) are not covered by SL. HMOs have separate license schemes not covered by this study.

Local authorities must obtain approval from national government if a proposed SL scheme covers >20% of their geographical area or affects >20% of privately rented homes in the local authority area. In this study, we will call these 'larger' SL schemes. SL schemes covering up to 20% can be implemented by local authorities without applying for this national government approval. We will call these 'smaller' SL schemes. The smaller schemes therefore have a simpler approval mechanism and they occur most frequently as zoned sub-areas within local authority boundaries.

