SL is a complex intervention situated within a multi-level complex system that includes tenants, properties, local and neighbouring areas and communities, landlords, property managers, other service-providers, housing markets, and local and national government. A characteristic of some complex systems is that benefits in one part of the system may contribute to harms or problematic outcomes elsewhere in the system. We hypothesise that this applies to the housing system. Some of these unintended consequences can be hypothesised in advance, while others may take us by surprise. What follows is a list of hypothesised unintended consequences we have thought about (we have given each a name, in capitals).

- 1. POLICY PRIORITY HYPOTHESIS. Some have argued that England's PRS is fundamentally flawed and that people are likely better off (and healthier) owning/mortgaging a home or using social housing [25]. An implication of this argument might be that even if SL does improve the PRS, it risks diverting policymakers away from policies to improve equitable access to the other sectors (e.g. through more affordable ways to buy, and more social housing).
- 2. AREA IMPROVEMENT HYPOTHESIS. If a place/locality improves, or is widely perceived to have improved, property values could increase. As a result, higher property prices would displace residents who cannot afford those prices.
- 3. HOME IMPROVEMENT HYPOTHESIS. If individual homes are improved, landlords may want to raise rents to reflect higher market values of improved properties.
- 4. PASSING COSTS ON TO TENANTS HYPOTHESIS. Landlords may raise rents to cover the costs of any mandated refurbishment and/or the license fee itself.
- 5. STOP RENTING HYPOTHESIS. Landlords may choose to stop renting property rather than pay for a license or improvements. Taking non-decent homes and poor landlords out of the PRS may be necessary for the sector's improvement but tenants could lose their home.
- 6. ASB DISCRIMINATION HYPOTHESIS. License conditions that oblige landlords to prevent and reduce ASB may be acted upon in ways that discriminate against certain groups.
- 7. ASB DISPLACEMENT HYPOTHESIS. Attempts to tackle ASB may displace rather than genuinely reduce ASB if antisocial tenants are obliged to live elsewhere.
- 8. POLARISATION HYPOTHESIS. Non-compliant landlords may be more likely to let to disadvantaged tenants, who have fewer housing options.

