### WP3 Cost-benefit analysis using subjective wellbeing approach

The economic evaluation will produce a cost-benefit analysis that uses the subjective wellbeing approach to monetise the benefits of SL. The starting point for the calculation of the benefits of SL will be the estimate of the impact of SL on the life satisfaction variable from the APS, one of our individual-level outcome measures. We will then follow the procedure described in Dolan et al. (2019) [35].

Essentially, we will use an estimate of the impact of income on life satisfaction from previous research to determine the income change that would be required to achieve the same change in life satisfaction as achieved by SL. Multiplying this income change amount by the number of individuals affected by SL will provide the total benefit of SL from a societal perspectives. All our calculations will be retrospective and estimate the benefits of SL over our 2012 to 2019 sample period. Depending on the results of our analysis of spillover effects, we will adjust the benefit estimate accordingly.

We will calculate the costs of SL from a public sector perspective and attempt to estimate the costs of SL from a societal perspective. To determine the total cost of SL from a public sector perspective over the 2012 to 2019 sample period, we will measure the direct and indirect cost of SL in four case study sites. Accounting data provided by the case study sites will be the starting point for the cost calculation. However, the economic concept of opportunity cost goes beyond accounting cost. For example, local authorities might employ staff specifically for the administration of the SL schemes in their area, so these costs would be included in the accounting data as staff salaries and on-costs. However, staff not specifically employed for SL purposes might also be involved in administering local schemes. Any staff involved in SL will require office space and might need to be trained and supervised. Local authorities need to disseminate information about their SL schemes using their website or other means and maintain the online application system. All these activities incur costs, either directly in the form of money being handed over in payment or indirectly in the form of resources such as staff time or office space not being available for alternative uses.

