The four case study sites have been selected to represent different types of SL (smaller and larger) in different regional contexts (north and south). We will use extrapolation methods that use these two broad characteristics as well as cost information obtained through FOI requests to assign costs to the other local authorities that have implemented SL. We will subtract income from license fees, fines and civil penalties to obtain net costs.

In addition, we will estimate the potential costs saved by the NHS through SL's impact on antidepressant prescribing, mental-health related hospital admissions and all-cause hospital admissions over our sample period. If possible, we will also estimate potential cost savings through impacts on mental health-related benefits. If we find substantial cost savings, we will subtract these from the cost of SL to local authorities to obtain net costs from a public sector perspective.

To estimate net costs from a societal perspective we will add back in any income local authorities generate from license fees, fines and civil penalties and try to estimate the costs landlords incur to remove hazards following the receipt of an improvement notice issued by the local authority following an SL inspection.

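### The societal cost-benefit rule leaves out landlords' extra rent, so a licence fee or counted repair cost passed on to tenants is charged as a cost and also deducted from the benefit

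*Protocol*

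**What the plan says.** The societal rule is in the WP3 part of Section 9a, in the same terms in the Protocol and the SAP.

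- **Benefit.** "The starting point for the calculation of the benefits of SL will be the estimate of the impact of SL on the life satisfaction variable" in the APS. That effect of selective licensing (SL) is turned into an equivalent income change. Then: "Multiplying this income change amount by the number of individuals affected by SL will provide the total benefit of SL from a societal perspectives". The only adjustment mentioned is for spillover.
- **Cost, authority side.** Fees, fines and penalties are first netted off for the public-sector view. Then: "To estimate net costs from a societal perspective we will add back in any income local authorities generate from license fees, fines and civil penalties". The authority's gross cost therefore counts.
- **Cost, landlord side.** The team will "try to estimate the costs landlords incur to remove hazards following the receipt of an improvement notice". No other landlord item appears, either as a cost or as income.

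Protocol Section 7c lists pass-through among its hypothesised unintended consequences (hypothesis 4): "Landlords may raise rents to cover the costs of any mandated refurbishment and/or the license fee itself". Hypothesis 3 adds that improved homes may command higher rents. Rent is a WP1 area-level outcome (Section 14a), but neither document links it to WP3.

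The WP3 text in Protocol Section 18 differs. It says "We will calculate the costs of SL from a public sector perspective", has no societal rule, and nets off fees only: "We will subtract income from license fees to obtain net costs".

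**The concern.** A rent rise caused by licensing moves money from tenants to landlords. For society as a whole it should net to zero. The plan applies that logic to the licence fee, a landlord-to-authority payment, by adding it back. It does not apply it to rent. The tenants' loss can enter through life satisfaction, while the landlords' gain enters nowhere.

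Two things follow if higher rent lowers life satisfaction. A fee or counted repair cost that is passed on is charged once in the cost and again as a smaller benefit. A rent rise beyond cost (hypothesis 3) is a pure transfer but counts as a net loss.

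The benefit-cost ratio is the WP3 outcome (Protocol Section 21). Its societal version would be biased against licensing in just the situation that hypothesis 4 describes, and a ratio modestly above 1 could be reported as below 1.

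**Working it through.** The documents state no ratio, pass-through share, authority cost or landlord cost, so there is no planned figure to reproduce. The check sets out accounts by party, per licensed home.

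**Inputs**

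- F, licence fee: "Fees vary but are around £600" for a five-year licence (Protocol Section 7a).
- G, authority's gross cost: not given. The Protocol says fees may fall short of it. Assumed F/G: 0.5 to 1.
- H, landlords' counted works: not given. Assumed £0 or £600.
- s, share of landlord cost passed on: not given. Assumed 0.5.
- v, pounds of measured benefit lost per pound of extra rent: not given. Section 18 of the Protocol illustrates the conversion with 0.5 points for £5,000, or 0.5/5,000 = 0.0001 points per pound. If rent acts like lost income, £1 of rent costs 0.0001 points, which converts back to £1, so v = 1. That is an assumption.
- B0, benefit before any rent effect: not given.

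**Accounts**, with rent passed on R = s(F + H)

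- Tenants: B0 − vR
- Landlords: R − F − H
- Authority: F − G

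At v = 1 these sum to B0 − G − H. The plan computes B0 − R − G − H, so its net benefit is too low by R.

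**Ratio.** The plan computes (B0 − vR)/(G + H). Against B0/(G + H), the shortfall in ratio points is

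v × s × (F + H)/(G + H).

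With s = 0.5, v = 1 and F = £600:

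| F/G | G | H | Shortfall |
|---|---|---|---|
| 1 | £600 | £0 | 300/600 = 0.50 |
| 1 | £600 | £600 | 600/1,200 = 0.50 |
| 0.75 | £800 | £0 | 300/800 = 0.375 |
| 0.75 | £800 | £600 | 600/1,400 = 0.43 |
| 0.5 | £1,200 | £0 | 300/1,200 = 0.25 |
| 0.5 | £1,200 | £600 | 600/1,800 = 0.33 |

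**Crediting convention.** Take G = £800, H = £600, B0 = £2,800, s = 0.5 and v = 1, so R = £600.

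- Plan: 2,200/1,400 = 1.57, net benefit £800.
- Rent credited on the benefit side: 2,800/1,400 = 2.00, net benefit £1,400.
- Rent netted from cost: 2,200/800 = 2.75, net benefit £1,400.

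The ratio depends on the convention; net benefit does not.

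**Dependence on v.** In the same example, the plan's ratio is 2.00 at v = 0, 2,500/1,400 = 1.79 at v = 0.5, and 1.57 at v = 1. Crediting the full £600 whatever v is gives 3,400/1,400 = 2.43, 3,100/1,400 = 2.21 and 2.00. A full credit therefore overshoots 2.00 unless v = 1. A credit of vR returns 2.00 in each case.

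**The case against.** The strongest objection is that v is unknown. Neither document says that rent lowers life satisfaction. The APS data are repeated cross-sections, so tenants who are priced out leave the sample and better-off entrants may replace them; measured life satisfaction need not fall by the amount of the rent rise. The rent outcome is advertised two-bedroom rent, which sitting tenants may not pay. Crediting it to every tenancy could replace a bias against licensing with one in its favour. This stands. It rules out a full rent credit as the sole base case and calls for a range over v. It does not justify omitting the item, because a method that values wellbeing through income cannot readily assume that rent has no effect.

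A second objection is that the societal costing is something the team will only attempt, that the stated purpose concerns local government resources, and that WP1 will report rent effects anyway. That lowers the urgency. A published societal ratio would still carry the bias.

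A reader might also infer that every licensing cost passed on is counted twice. The documents do not support that. Voluntary upgrades, and works that cannot be costed, are not in the societal cost, so passing them on is counted once. Nor does hypothesis 2 help: it speaks of property values and prices displacing residents, not of rents.

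**Conclusion.** The point holds for the societal calculation in Section 9a of both documents. The direction is clear: the ratio is too low whenever licensing raises rent and higher rent lowers measured life satisfaction. The size is v × s × (F + H)/(G + H) ratio points for passed-on fees and counted works: 0.25 to 0.50 under the assumed values, and zero if v = 0. The formula leaves out NHS savings; subtracting them would shrink the denominator and enlarge the shortfall.

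Three stronger readings are not supported:

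- That the ratio falls by exactly the pass-through share. In ratio points this needs v = 1 and fees that fully recover the authority's cost.
- That the public-sector version has the same fault. It subtracts fees, so a passed-on fee is not counted twice there.
- That a national sum follows from the £600 fee and the 777,688 private renters in Table 2. The documents give no household size. Houses in multiple occupation are outside SL. Only 637,541 of those renters live in fully covered LSOAs. By Table S1, 423 of 1,635 LSOAs (26%) were first licensed in 2018 or 2019, so most of a five-year licence there falls outside the 2012 to 2019 window.

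**What to change.** In the WP3 part of Section 9a, in both documents:

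- State that rent changes caused by licensing are tenant-to-landlord transfers.
- Report the societal result without a rent credit and with one. Place the credit on the benefit side as a fixed convention, and set it to v times the extra rent so that the transfer nets to zero.
- Show it at zero, WP1-estimated and full pass-through, for v below 1 and at 1.
- Report societal net benefit alongside the ratio.
- Limit the credit to licensed tenancies and licensed time within 2012 to 2019. The rent series ends in 2018, so state the assumption used for 2019.

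Leave the fee treatment in the public-sector version as it is, but reconcile Protocol Section 18 with Section 9a: they differ on whether there is a societal perspective and on whether fines and penalties are netted off.

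The cost is a few sentences and a few lines of calculation that use a rent effect WP1 already estimates. The downside is that this effect rests on advertised two-bedroom rents for 2012 to 2018, so the societal ratio becomes a range. The rule should be fixed before outcome analysis, as the SAP intends for its methods, so that it cannot appear to have been chosen from the results.
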